6.4 Further Analyses

Follow-up analyses to report further efficacy and safety data will be done once all participants have completed the 1-year follow-up period and at the end of study.

Additional analyses of safety and preliminary antitumor activity might be performed for the purpose of publication at scientific congresses.

7 Changes to the Planned Analyses in the Clinical Study Protocol

Outcome of the tumor assessment prior to surgery is reflected in the analysis of cCR. As the number of subjects in the dose escalation cohorts is low, PK exposure of peosertib versus safety and exposure will not be performed.

7.1 COVID-19 Impact

Additional listings will be generated to assess potential impacts of COVID-19 to this study including:

- listing of participants potentially affected by pandemic and with any AEs or PDs related to COVID-19
- listing of PDs related to COVID-19
- listing of AEs related to COVID-19.

8 Protocol Deviations and Analysis Populations

8.1 Definition of Protocol Deviations and Analysis Populations

Important protocol deviations are protocol deviations that might significantly affect the completeness, accuracy, and/or reliability of the study data or that might significantly affect a participant's rights, safety, or well-being.

The following deviations will be identified and confirmed prior to or at the data review meeting, at the latest.

Important protocol deviations will be categorized into one of the following:

- Subject enrolled and dosed on the study who did not satisfy enrolment criteria
- Subject fulfills withdrawal criteria whilst on the study but is not withdrawn

- Subject is administered the wrong study intervention or an incorrect dose
- Subject is administered or takes concomitant medication excluded by the clinical study protocol (CSP)
- Failure to collect data necessary to interpret primary endpoints
- Failure to collect necessary key safety data
- Deviations from good clinical practice (e.g. deviations related to informed consent of study participants)
- Any other protocol deviation that might significantly affect the completeness, accuracy, and/or reliability of the study data or that might significantly affect a participant's rights, safety, or well-being

All important protocol deviations are listed in a separate document. In addition, all important protocol deviations are documented in study data tabulation model (SDTM) datasets whether identified through site monitoring, medical review or programming.

8.2 Definition of Analysis Populations and Subgroups

The analysis populations are specified below:

Table 1 Description of Analysis Sets

Population	Description
Enrolled	All participants who sign informed consent
Dose escalation (DE)	The DE Analysis Set will include all participants treated in dose escalation cohorts, who receive at least 80% of peposertib, 50% of capecitabine, and 80% of RT planned dose and complete the DLT period (5 or 5.5 weeks after start of treatment or for the entire duration of the treatment). The DE set will also include participants treated in dose escalation cohorts who experience a DLT during the DLT period regardless of the amount of each study intervention received/completion of the DLT period.
Full analysis set (FAS)	The FAS will include all participants who are enrolled in the study and received at least 1 dose of study intervention.
Safety (SAF)	The SAF analysis set will include all participants who receive at least 1 dose of study intervention. Participants will be analyzed according to the actual treatment they receive. In case of different doses received the dose with high number of administrations will be used as actual treatment.
Pharmacokinetics (PK)	The PK analysis set is defined as all participants who receive at least 1 dose of peposertib and have sufficient peposertib plasma concentration data to enable the calculation of at least 1 PK parameter. Sufficient concentration data is defined as at least 3 valid, post dose, concentration points in the PK profile to obtain any PK parameter.

DE=dose escalation, DLT=dose limiting toxicity, FAS=full analysis set, PK=pharmacokinetic, RT=radiotherapy, SAF=safety

Table 2 Summary of Analyses and associated Analysis Set

Analyses	ENR	SAF	FAS	DE	PK
Disposition	✓				
Baseline assessments		✓			
Past and concomitant therapies		✓			
Compliance and exposure		✓			
Primary endpoint: DLTs				✓	
Efficacy			✓		
Safety and tolerability		✓			
CCI					
Pharmacokinetics					✓
CCI					

DE=dose escalation, ENR=enrolled, FAS=full analysis set, PK=pharmacokinetic, SAF=safety

9 General Specifications for Data Analyses

Study intervention groups

Unless otherwise indicated all analyses will be presented separately for each dose level, and overall.

Data handling after cut-off date

Data after cut-off do not undergo the cleaning process, will not be included in SDTMs, and will not be displayed in any listings or used for statistical analyses or imputation.

Stop dates are not affected by this rule, e.g. a stop date of AEs, which starts prior to the cut-off, but stops after date of cut-off, will not be changed.

Significance level

All statistical tests mentioned in this IAP are to be regarded as exploratory. All statistical tests comparing study intervention groups will be performed two-sided. If confidence intervals are to be calculated, these will be two-sided with a confidence probability of 95%, unless otherwise specified in the corresponding section of this IAP.

Presentation of continuous and qualitative variables

Continuous variables will be summarized using descriptive statistics, i.e.

- number of participants, number of participants with non-missing values,

- mean, standard deviation,
- median, 25th Percentile - 75th Percentile (Q1-Q3),
- minimum, and maximum.

Qualitative variables will be summarized by counts and percentages.

Unless otherwise stated the calculation of proportions will be based on the number of participants in the analysis population of interest. Therefore, counts of missing observations will be included in the denominator and presented as a separate category.

For summaries by visits, only visits where all subsequent visits have 3 or more participants will be displayed. In case the analysis refers only to certain visits, percentages will be based on the number of participants in the corresponding analysis set.

Presentation of PK concentration data

Peposertib, its metabolite (if available), capecitabine, and its metabolite (if available) concentration data will be descriptively summarized using: number of non-missing observations (n), arithmetic mean (Mean), standard deviation (Sd), coefficient of variation (CV%), minimum (Min), median (Median), and maximum (Max). If $n \leq 2$, only n, Min, and Max will be reported.

Descriptive statistics of PK concentration data will be calculated using values with the same precision as the source data, and rounded for reporting purposes only. The following conventions will be applied when reporting descriptive statistics of PK concentration data:

Mean, Min, Median, Max: 3 significant digits

Sd: 4 significant digits

CV%: 1 decimal place

Presentation of PK parameter data

Pharmacokinetic parameter data will be descriptively summarized using: n, Mean, Sd, CV%, Min, Median, Max, geometric mean (GeoMean), and the geometric coefficient of variation (GeoCV) and the 95% confidence interval for the GeoMean (LCL 95% GM, UCL 95% GM). For time to reach maximum observed concentration (t_{max}), only n, Min, Median, and Max will be reported.

If $n \leq 2$, only n, Min, and Max will be reported.

The PK parameter maximum observed plasma concentration (C_{max}) will be reported with the same precision as the source data. All other PK parameters will be reported to 3 significant figures. In export datasets, as well as in the SDTM and ADaM PP domain, PK parameters will be provided with full precision, and will not be rounded. Descriptive statistics of PK parameter data will be calculated using full precision values and rounded for reporting purposes only.

CONFIDENTIAL
INFORMATION

CCI
CCI

17/66

The following conventions will be applied when reporting descriptive statistics of PK parameter data:

Mean, Min, Median, Max, GeoMean, 95% CI: 3 significant digits

Sd: 4 significant digits

CV%, GeoCV%: 1 decimal place

Study day

Study day (also called treatment day) is defined relative to the date of start of treatment (first administration of peposertib, RT, or capecitabine, whatever is earliest). Study day 1 defines the day of first treatment, the day before is defined as study day -1 (no study day 0 is defined).

Definition of baseline

The last measurement prior to first administration of trial treatment (either peposertib, RT or capecitabine) will be used as the baseline measurement. If an assessment is planned to be performed prior to the first dose of study treatment in the protocol and the assessment is performed on the same day as the first dose of study treatment, it will be assumed that it was performed prior to study treatment administration, if assessment time point is not collected or is missing. If assessment time points are collected, the observed time point will be used to determine pre dose on study day 1 for baseline calculation. Unscheduled assessments will be used in the determination of baseline. However, if time is missing, an unscheduled assessment on study day 1 will be considered to have been obtained after study treatment administration.

Definition of change from baseline (per visit)

Change from baseline: visit value – baseline value

Percent change from baseline: $100 * (visit value - baseline value) / baseline value$

Definition of on treatment period:

On treatment period is defined as the time from the first administration of study intervention to the last administration of study treatment + 30 days, or the clinical cut-off date (if the treatment is still ongoing), or death, whichever occurs first.

Date of last known to be alive

The date of last known to be alive will be derived for participants not known to be dead at the analysis cut-off using the latest complete date among the following:

- All subject assessment dates:

- Laboratory assessments using information from “Hematology”, “Biochemistry”, “Coagulation”, “Urinalysis”, “Pregnancy test” and “Creatinine Clearance” eCRF pages (LBDTC variable from LB SDTM domain to be used)
- Vital signs using information from “Vital signs” eCRF page (VSDTC variable from VS SDTM domain to be used)
- Performance status using “ECOG Performance status” eCRF page (QSDTC variable from QS SDTM domain to be used)
- ECG, using information from both local and central ECGS (EGDTC variable from EG SDTM domain to be used)
- Tumor assessments using “Tumor assessments” eCRF pages (TRDTC/TUDTC variable from TR/TU SDTM domain to be used)
- Surgery information using “Rectal Surgery at week 15”, “Rectal Surgery after Week 15”, “Surgery after discontinuation” eCRF pages
- Anti-cancer treatment after discontinuation start and end date from “Anti-Cancer treatment after discontinuation” eCRF page.
- Start dates of concomitant medications or anti-cancer therapies administered after study treatment termination using “Concomitant medications”, “Anti-cancer treatment after discontinuation details” eCRF pages (CMSTDTC variable from CM SDTM domain to be used)
- AE start dates from “Adverse events details” eCRF page (AESTDTC variable from AE SDTM domain to be used)
- Study treatment administration dates using “M3814 (PEPOSERTIB)/PLACEBO Administration Details”, “RT Administration” and “Capecitabine Administration” eCRF pages (EXSTDTC variable from EX SDTM domain to be used)
- Last known to be alive date using “Survival Follow-up page” (SSDTC variable from SS SDTM domain where SSCAT=“SURVIVAL FOLLOW-UP”), where status is “Alive”.

Only dates associated with actual examinations of the participant reported in the eCRF will be used in the derivation. Dates associated with a technical operation unrelated to participant status (such as the date a blood sample was processed) will not be used. Assessment dates after the cut-off date will not be considered for derivation of last date known to be alive.

Definition of duration/ time since an event

Duration will be calculated by the difference of start and stop date + 1 (e.g., survival time [days] = date of death – date of Study day 1 + 1), if not otherwise specified.

The time since an event (e.g. time since first diagnosis) will be calculated as date of event – Study day 1 + 1.

Conversion factors

The following conversion factors will be used to convert days into months or years: 1 month = 30.4375 days, 1 year = 365.25 days.

Handling of missing data

Unless otherwise specified, missing data will not be replaced.

In all participant data listings imputed values will be presented, and the imputed information will be flagged (if not specified otherwise).

Missing statistics, e.g., when they cannot be calculated, should be presented as “nd” (not done). For example, if n=1, the measure of variability (Sd) cannot be computed and should be presented as “nd”.

Adverse events

For identification of AE treatment emergence, incomplete dates will be handled as follows:

- In case the onset date is completely missing, or the onset is in the same year (if the onset year is available only) or the onset is in the same month and year (if the day is missing) as start of trial treatment then the onset date will be replaced either by the start of trial treatment date or the AE resolution date, whichever is the earliest.
- In all other cases, the missing onset day or onset month will be replaced by 1.
- Incomplete stop dates will be replaced by the last day of the month (if day is missing only), if not resulting in a date later than the date of subject’s death. In the latter case, the date of death will be used to impute the incomplete stop date.
- In all other cases, the incomplete stop date will not be imputed.

Previous/Concomitant medication

For identification of previous or concomitant medications/procedures, no formal imputation will be performed on missing or incomplete dates. Table 3 indicates whether a treatment is considered to be stopped before or after start of treatment. Rules presented in [Table 4](#) will be used to define if a medication/procedure is considered as a previous, concomitant or both previous and concomitant medication/procedure.

Table 3 Stopping rules for medication/procedure end dates

End date of medication/procedure			Stopping rule
Day	Month	Year	
UNK	UNK	UNK	After treatment start (ongoing)
UNK	UNK	< Treatment start (year)	Before treatment start
UNK	UNK	>= Treatment start (year)	After treatment start
		< Treatment start (month and year)	Before treatment start
		>= Treatment start (month and year)	After treatment start
		< Treatment start (complete date)	Before treatment start
		>= Treatment start (complete date)	After treatment start

UNK = Unknown

Table 4 Rules to define previous and/or concomitant medications

Start date of medication/procedure			Stopping rule (see Table 3)	Medication/ procedure
Day	Month	Year		
UNK	UNK	UNK	Before treatment start	Previous
UNK	UNK	UNK	After treatment start	Previous and concomitant
UNK	UNK	<= Treatment start (year)	Before treatment start	Previous
UNK	UNK	<= Treatment start (year)	After treatment start	Previous and concomitant
UNK	UNK	> Treatment start (year) and <= Treatment end + 30 days (year)	After treatment start	Concomitant
UNK		<= Treatment start (month and year)	Before treatment start	Previous
UNK		<= Treatment start (month and year)	After treatment start	Previous and concomitant
UNK		> Treatment start (month and year) and <= Treatment end + 30 days (month and year)	After treatment start	Concomitant
		<= Treatment start (date)	Before treatment start	Previous
		<= Treatment start (date)	After treatment start	Previous and concomitant
		> Treatment start (date) and <= Treatment end + 30 days (date)	After treatment start	Concomitant

UNK = Unknown

Tumor assessments

Tumor response assessments will be based on MRI, endoscopic and digital rectal evaluation (DRE). All investigation dates (e.g. MRI, endoscopy, DRE) must be completed with day, month and year.

If there are multiple dates associated with an evaluation, i.e., radiological assessments occur over a series of days rather than the same day, the choice of date of assessment could impact the date of progression and/or date of response. If there are multiple dates associated with an evaluation, the earliest of the dates associated with the evaluation will be used as the date of assessment.

If one or more investigation dates for an evaluation are incomplete but other investigation dates are available, the incomplete date(s) are not considered for calculation of the assessment date, and assessment date is calculated as the earliest of all investigation dates (e.g. MRI, endoscopy, DRE).

If all measurement dates for an evaluation have no day recorded, the first of the month is used.

If the month is not completed, for any of the investigations for an evaluation, the respective assessment will be considered to be at the date which is exactly between the previous and the following assessment. If the previous or the following assessment is not available, the assessment in between will not be used for any calculations.

Death date

For imputing missing day of death date, if month and year is available, the day will be imputed by 15, unless this results in a date not later as a date the participant is known to be alive. In that case the date of death will be imputed by the last date known to be alive + 1.

Start/stop date of subsequent anti-cancer therapy

Incomplete dates for start date of subsequent anti-cancer therapy (drug therapy, radiation, surgery) will be imputed as follows:

- If only day is missing, it will be imputed as the last day of the month unless the end date of subsequent anti-cancer therapy is before that date. In that case, the incomplete anti-cancer therapy start date will be imputed as the end date of the anti-cancer therapy.
- If both day and month are missing, no imputation will be performed.

Incomplete subsequent anti-cancer therapy stop dates will not be imputed.

Categorization of participants for COVID-19 impact assessment

For the assessment of COVID-19 impact on this study, participants will be categorized as being potentially affected by COVID-19 based on the COVID-19 pandemic start date.

This date is defined as the minimum of the first COVID-19 death date per country and 11 March 2020 (WHO-start of world-wide pandemic). First death from COVID-19 per country is determined according to the published data by European Centre for Disease Prevention and Control (Status of 26 June 2020).

If the pandemic start is before the end of DLT period, both DLT and FUP periods for the subject will be considered as potentially affected. If it starts during the FUP period, only this period will be considered as potentially affected.

Software

All statistical analyses will be performed using SAS® Software version 9.4 or higher. Non-compartmental computation of PK parameters will be performed using the computer program Phoenix® WinNonlin® Version 8.0 or higher (Pharsight Corporation, a Certara Company, Princeton, New Jersey).

10 Study Participants

The subsections in this section include specifications for reporting participant disposition and study intervention/study discontinuations. Additionally, procedures for reporting protocol deviations are provided.

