1.3 Schedule of Activities

The treatment period will include 25 or 28 RT fractions, depending on local practice.

- The Schedule of Activities (SoA) is provided in [Table 1](#).
- The SoA for the Long-term Safety Follow-up is provided in [Table 2](#).
- **CCI** [REDACTED]
- The PK sampling schedule is provided in [Table 4](#).
- **CCI** [REDACTED]

Table 1 Schedules of Activities – 25 or 28 Fraction Days

		Evaluation Period											Notes
Study Period	Screening	Treatment Period/DLT Period (peposertib + capecitabine + RT)								Short-term Safety FU			Capecitabine given within 30 min after meal (AM and PM dosing), peposertib given 1 h after meal, RT given 1.5 h (\pm 30 min) after M3814 dosing. See Table 7 and Section 6.6.2.4.
Study Day	Day -28 to -1	FD1 to 25 or 28 Visits: on all FD (FD1 to FD25 or 28), FD25 or 28 is last RT day											
Peosertib Capecitabine RT		X: Peosertib qd 5 d/wk (only on FD) X: Capecitabine 825 mg/m ² bid 5 d/wk (only on FD) X: RT 1.8 Gy/fraction, 5 FD/wk, integrated concomitant boost (total daily dose 2 Gy) is allowed									Surgery		
Visit Week	-4 to -1	1	1	2	2	3	4	5	5 or 6	7 to 14	15	19	
Visit Day	-28 to -1	FD1	FD2	FD6	FD9	FD11	FD16	FD21	FD25 or FD28/ETT	In case of acute toxicities one visit/wk until recovery ^{a,b}	One visit / wk		If premature discontinuation during treatment, the SoA for FD25/FD28 should be performed. In such cases, this visit will be considered the ETT visit. ^a Where recovery means until the toxicity reduces to Grade 1 or to baseline Wk 14 visit is mandatory. ^b In case of a pandemic, it is per Investigator's discretion if these visits can be done via a phone call. Wk 14 visit remains a clinic visit.
Visit Window (Days)										\pm 7 for Wk 14 only/ \pm 2 for other visits	\pm 14	\pm 14	

Assessments and Procedures

Signed ICF	X												
Inclusion/Exclusion Criteria	X	X											
Demography	X												
Medical History	X												

		Evaluation Period											Notes
Study Period	Screening	Treatment Period/DLT Period (peposertib + capecitabine + RT)								Short-term Safety FU			Capecitabine given within 30 min after meal (AM and PM dosing), peposertib given 1 h after meal, RT given 1.5 h (± 30 min) after M3814 dosing. See Table 7 and Section 6.6.2.4.
Study Day	Day -28 to -1	FD1 to 25 or 28 Visits: on all FD (FD1 to FD25 or 28), FD25 or 28 is last RT day											

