4.1.2 Treatment Period

The starting dose of peposertib for the first cohort will be 50 mg once daily (Section 4.3). Participants for next cohorts will be assigned to an peposertib dose determined by the SMC. The SMC dose recommendations will be guided by a Bayesian 2-parameter logistic regression model with overdose control (Appendix 10). The planned cohort size is 3 participants. Peposertib will be given in combination with capecitabine at a dose of 825 mg/m² twice daily and RT of 50 to 50.4 Gy to the tumor area and 45 Gy to the electively irradiated tissues in 25 or 28 fractions (corresponding to 5 to 5.5 weeks). Full details of the dosing regimens are provided in Section 6.6.2.

After each cohort has completed the 5 to 5.5-week treatment period (DLT period), the SMC will review safety, including DLT data, tolerability, and PK data if available, and will recommend the peposertib dose for the next cohort. In addition, any toxicities observed during the Short-term Safety Follow-up will be reviewed and considered by the SMC for the overall evaluation of the safety and proposal of dose escalation of peposertib. Dose limiting toxicities are defined in Section 6.6.1. If the SMC decides to escalate the dose for the next cohort, it is in exceptional cases at discretion of the study team (medical lead and safety lead with input from statistician) to include up to 3 further participants in parallel, on a dose level that has already been tested in a previous cohort.

Participants will receive CRT until treatment completion after 25 or 28 RT fractions or disease progression, unacceptable toxicity or participant refusal to continue.

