6.6 Dose Selection and Modification

Physician discretion may be used if monitoring or dose modification outside of the guidelines is considered necessary.

If participants vomit after taking their dose of peposertib and/or capecitabine, they should be given an antiemetic but the dose(s) will not be replaced. Prophylactic antiemetics should then be considered prior to subsequent doses of peposertib and/or capecitabine. Any change from dosing schedule, dose interruptions, or dose reductions should be recorded in the eCRF.

In general, each participant will stay on the peposertib, and capecitabine dose level assigned in the study unless treatment needs to be interrupted, modified or stopped. If peposertib dosing interruptions are necessary, the SMC may decide to start the next cohort at a lower dose level or at a lower dosing intensity (e.g. three times weekly or twice weekly).

If 1 study intervention must be withheld, that study intervention's dose should be skipped rather than delayed, and the other study intervention (capecitabine or peposertib) should be given alone.

If hemoglobin is < 8 g/dL then appropriate measures according to standard clinical practice must be taken prior to any further dose administration.

The SMC will be responsible for dose escalation decisions and will provide input into the selection of a RP2D. Details of SMC decision making processes are provided in [Appendix 2](#). The DLT definition is provided in Section [6.6.1](#).

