$$\text{Relative dose intensity (\%)} = \left(\frac{\text{cumulative dose (Gy)}}{x * \text{planned daily dose (Gy)}} * 100 \right)$$

- For capecitabine:

$$\text{Relative dose intensity (\%)} = \left(\frac{\text{cumulative dose (mg/m}^2\text{)}}{x * \text{planned daily dose (mg/m}^2\text{)}} * 100 \right)$$

Where planned daily dose (mg/m²) is the sum of planned doses per day . Each fraction day, the planned daily dose (mg/m²) is derived as:

$$\text{Planned daily dose} = \text{Planned morning dose (mg/m}^2\text{)} + \text{Planned evening dose (mg/m}^2\text{)}$$

For all 3 relative intensity formula above, x = 25 or 28, depending on the number of fraction doses the participant received.

The relative dose intensity will be displayed using the following categories:

- > 110%
- [80% - 110%]
- [65% - 80%[
- [50% - 65%[
- < 50%

Statistical outputs

The treatment exposure and compliance will be summarized in 4 tables including informations for each study treatment (peposertib /RT/capecitabine).

The first table will summarize the duration in weeks of each treatment (peposertib /RT/Capecitabine), by displaying the number of participants by dose level in each of the following categories:

- < 2 weeks
- [2 - 4 weeks[
- [4 - 6 weeks[

- ≥ 6 weeks

The table will also display summary statistics of the duration in weeks of each treatment.

The second table will summarize the number of total administrations of each treatment (peponsertib /RT/capecitabine), by displaying the number of participants by dose level in each of the following categories:

- < 10 administrations/fraction days (peponsertib /RT)
-]10 -20 administrations/fraction days] (peponsertib /RT)
-]20 - 25 administrations/fraction days] (peponsertib /RT)
-]25 - 28 administrations/fraction days] (peponsertib /RT)
- > 28 administrations/fraction days (peponsertib /RT)

The categories to display for cisplatin are:

- ≤ 20 administrations
-]20 - 40 administrations]
-]40 - 56 administrations]
- > 56 administrations.

The third table will summarize the cumulative dose, dose intensity and relative dose intensity for each treatment.

The fourth table will summarize dose reductions by dose level, with for each treatment (peponsertib /RT/capecitabine):

- Number of participants without any dose reduction
- Number of participants with at least one dose reduction
- Number of participants who did not receive this study intervention

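### The safety set labels a participant by the peposertib dose taken most often, so an early dose reduction moves that participant's toxicity to the lower dose column

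*SAP*

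**What the plan says.** The safety row of SAP Section 8.2, Table 1, first sets an as-treated principle: "Participants will be analyzed according to the actual treatment they receive". It then gives the rule for mixed dosing: "In case of different doses received the dose with high number of administrations will be used as actual treatment". I read this as the dose with the most administrations.

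SAP Section 9 adds: "Unless otherwise indicated all analyses will be presented separately for each dose level, and overall". The exposure, adverse event, laboratory, vital sign and ECG sections (SAP 13 and 15) all use the safety set. I found no rule that places an event under the assigned dose or under the dose at onset.

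The combined FAS/SAF row of protocol Table 11 has no most-frequent-dose rule, and SAP Section 7 does not list one among the changes from the protocol.

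On dose changes, protocol 6.6 says: "In general, each participant will stay on the peposertib, and capecitabine dose level assigned in the study unless treatment needs to be interrupted, modified or" (the last item in that list is the end of treatment). It also says: "Physician discretion may be used if monitoring or dose modification outside of the guidelines is considered necessary". Dose reductions are to be recorded in the eCRF. For each study treatment, including peposertib, the fourth exposure table in SAP Section 13 counts: "Number of participants with at least one dose reduction". Protocol 6.6.2.1 does not permit escalation within a participant.

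**The concern.** In a dose escalation study, a safety table by dose level should show what happened to participants started at each dose. The most-frequent-dose rule makes the column depend on something that happens after treatment starts. The participants it moves are those whose dose was changed, and one reason to reduce a dose is toxicity at that dose. Because escalation within a participant is barred, any protocol-compliant change is downward. The rule can therefore take events out of the higher dose column and add them to the lower one, but not the reverse.

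At stake is the secondary objective on safety and tolerability, which is reported by dose level with very few participants per level. SAP Section 6.2 also plans an analysis of key safety and efficacy endpoints to inform further development.

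**Working it through.** The documents give no figure to reproduce here, so the check is a direct count.

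**Inputs**
- Planned peposertib administrations F, once daily on fraction days: 25 or 28. Protocol 1.3: "The treatment period will include 25 or 28 RT fractions, depending on local practice".
- Cohort size, protocol 4.1.2: "The planned cohort size is 3 participants".
- DLT criterion 5 (protocol 6.6.1): related toxicity that leaves the participant with less than 80% of the planned dose.
- Relative dose intensity for peposertib (SAP 13): cumulative dose / (x × dose level), with x = 25 or 28.

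**When the label changes.** Let k be the administrations at the assigned dose and F − k those at the reduced dose. The label moves to the lower dose if F − k > k, that is, k < F/2.

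| Schedule | No missed doses | With 5 skipped doses (assumption) |
|---|---|---|
| 25 | k ≤ 12 | k ≤ 9 of 20 |
| 28 | k ≤ 13 | k ≤ 11 of 23 |

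With no missed doses, the first reduced dose must therefore fall by FD13 (25 fractions) or FD14 (28 fractions). On 28 fractions, k = 14 gives 14 against 14, for which there is no rule. A later reduction leaves the participant under the assigned dose.

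**Effect on a by-dose table.** Assume cohorts of 3 at 200 mg and 100 mg. One participant has a Grade 3 event at 200 mg and takes 100 mg after 8 of 25 administrations. Since 17 > 8, the participant is labelled 100 mg.

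| Basis | 200 mg | 100 mg |
|---|---|---|
| Assigned dose | 1/3 (33%) | 0/3 (0%) |
| SAP rule | 0/2 (0%) | 1/4 (25%) |

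The apparent order of the two doses is reversed. The dose-reduction table is also a safety-set table by dose level, so the reduction from 200 mg would be counted at 100 mg.

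**Effect on relative dose intensity.** Cumulative dose = 8 × 200 + 17 × 100 = 3300 mg.
- Against the assigned dose: 3300 / (25 × 200) = 66%.
- If dose level is read as the most frequent dose: 3300 / (25 × 100) = 132%, which falls in the SAP category above 110%.

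The SAP does not say which reading applies.

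**Overlap with the primary analysis.** For a halved dose, the largest share of planned dose among relabelled participants is (12 + 0.5 × 13)/25 = 74.0%, or (13 + 0.5 × 15)/28 = 73.2%. Both are below 80%. If related toxicity was the cause, criterion 5 is met, subject to SMC confirmation, and the participant enters the dose escalation set. For a smaller step this need not hold. With 250 mg reduced to 200 mg after 5 of 25 administrations, the share is (5 × 250 + 20 × 200)/(25 × 250) = 84.0%, so relabelling can occur without criterion 5.

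**The case against.** The strongest reply is that the case is rare and largely covered elsewhere. For systemic toxicity, protocol Table 10 has peposertib interrupted and resumed at the same dose, or discontinued; it has no reduction step. Interruption alone does not create a second dose, because SAP Section 13 counts only doses above zero. A reduction therefore needs the discretion allowed in protocol 6.6. The dose-reduction table is one generic list for all three treatments, so it is weak evidence that peposertib reductions were expected. No actual reduction is documented. The diarrhea management charter is not among the documents, so its content is unknown. When a reduction does occur, the adverse event listing shows dates, grade, DLT flag and action taken, the exposure listing shows planned and actual doses, and the overall columns are unaffected.

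All of this stands and limits the size of the point. It does not remove it: the rule has a function only when doses differ within a participant, and listings let a reader trace a moved case but leave the summary tables as they are.

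A reader might infer three stronger things that the documents do not support:
- *Any toxicity followed by a reduction is reported under the lower dose.* This is so only if the lower dose then has more administrations than the assigned one.
- *The rule distorts the MTD or RP2D.* The DLT analysis and the Bayesian model use the dose escalation set (protocol 9.4.2; SAP 15.1), for which this rule is not stated. Enrolment is closed, treatment is complete and Phase II will not be run.
- *The error always runs one way.* This holds for protocol-compliant changes. Incorrect doses and overdoses, which both documents foresee in some form, could move a participant in either direction.

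**Conclusion.** The point holds for the secondary safety and exposure tables by dose level. The rule conditions the dose column on what happens during treatment. For protocol-compliant changes, its bias runs only from the higher to the lower dose. It acts when peposertib is reduced with at most 12 of 25 or 13 of 28 administrations at the assigned dose, assuming none missed. One such participant in a cohort of 3 can turn 1/3 into 0/2; that example is hypothetical, and the number of participants affected may be zero.

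The primary DLT table is not shown to be affected. However, the SAP does not say whether dose level there means assigned or actual dose. If it means assigned dose, one participant could be a DLT at one dose and an adverse event case at another. The change is worth making, but the trial's primary conclusion does not depend on it. Nothing here is a view on which dose-modification rule is clinically right.

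**What to change.** Replace the last two sentences of the safety row in SAP Table 1 with:

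*Participants are analysed under the peposertib dose level of their assigned cohort; if the dose received on FD1 differed from the assigned dose, the dose received on FD1 is used. Later dose changes do not alter the dose level and are shown in the exposure tables and listings.*

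Use the same basis for dose level in the dose escalation set and for the denominator of peposertib relative dose intensity. List the dose-labelling rule in SAP Section 7, since protocol Table 11 has none. The new wording also makes a tie rule unnecessary.

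The cost is a few sentences of text, and results do not change for anyone who stayed on the assigned dose throughout. The downside is that a participant who took mostly the lower dose is shown under the higher one; the exposure tables make that visible. Treatment is already complete and the study is open-label, so the change and its reason should be dated and documented.
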